8.2.8 Interim Analysis

Access to Unblinded Reports

The independent eDMC will routinely evaluate unblinded safety analyses of all trial subjects while the initial 78 week trial is blinded. Additional safety analyses may be conducted throughout the trial as requested by the eDMC. The sponsor will be unblinded after completion of the initial 78-week trial.

8.3 Safety Analysis

Subjects from all three arms (40 mg / 40 mg, 12 mg / 12 mg, Pbo / 40 mg) will be included in the safety analyses (with any subject treated with MK-8931 60 mg still excluded from the primary analysis). Where applicable, treatment comparisons will be conducted between the 40 mg / 40 mg and Pbo / 40 mg arms, as well as between the 12 mg / 12 mg and Pbo / 40 mg arms.

The broad clinical and laboratory AE categories consisting of the percentage of subjects with any AE, with a drug related AE, with an SAE, with an AE which is both drug-related and serious, or who discontinued because of an AE are considered as Tier 2 endpoints and will be analyzed. Descriptive Safety Endpoints are considered as Tier 3 events and will also be analyzed.

Analyses will be conducted both on the cumulative data including data from the initial 78-week trial as well as this long term safety trial, no analyses will be conducted on the long term safety trial alone.

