- The Full Analysis Set (FAS) population will serve as the primary population for the analysis of efficacy data in this trial.
- The All-Patients-as-Treated (APaT) population will be used for the analysis of safety data in this trial. The APaT population consists of all randomized subjects who received at least one dose of trial treatment, with subjects included in the treatment group corresponding to the trial treatment they actually received.
- It is noted that the first 200 subjects enrolled will be excluded from the primary efficacy and safety analyses, since the siDMC will have access to unblinded data from these subjects in advance of a dose decision.

Efficacy Analysis:

There are no formal hypotheses for this trial. All efficacy measurements analyzed during the initial 78 week trial will continue to be collected and analyzed in the long term safety trial. The primary endpoint is the 24-Month (6 months after the primary timepoint from the initial 78 week trial) change-from-baseline treatment difference on ADAS-Cog and ADCS-ADL.

Safety Analysis: Safety and tolerability will be assessed by a clinical review of all relevant parameters including adverse events (AEs), laboratory tests, vital signs, and ECG measurements.

[figure not shown]
Safety analyses will be conducted on the cumulative data from the initial 78-week trial pooled with the data from the long term safety trial; no analyses will be conducted on the long-term safety data alone.

The broad clinical and laboratory AE categories consisting of the percentage of subjects with any AE, with a drug related AE, with an SAE, with an AE which is both drug-related and serious, or who discontinued because of an AE are considered as Tier 2 endpoints and will be analyzed. Descriptive Safety Endpoints are considered as Tier 3 events and will also be analyzed.

Interim Analyses: There are no planned interim analyses for this long-term safety trial. (The Sponsor will be unblinded following the completion of the initial 78 week trial. Some Sponsor personnel will remain blinded during the long-term trial, as necessary, to support the conduct of the trial and the collection of efficacy data.)

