5.4 Outcome Measures Rationale

The primary clinical measures in this trial are the Alzheimer's Disease Assessment Scale Cognitive subscale (ADAS-Cog) and the Alzheimer's Disease Cooperative Study Activities of Daily Living Inventory (ADCS-ADL). The ADAS-Cog is a measure of cognition while the ADCS-ADL is a measure of functional ability in activities of daily living. The measures are validated instruments that are acceptable to regulatory agencies, have been used previously in drug trials in this patient population, and can reliably detect clinically relevant changes in AD.

After the initiation of P017, the FDA issued guidance to Sponsors indicating that all trials with BACE1 inhibitors that are longer than two weeks in duration must include routine monitoring of skin. There have been observations in the literature that mice lacking the gene for BACE2 have reduced pigment [30]. In recently completed studies of MK-8931 in two pigmented species (mouse and rabbit), reduced hair pigment was observed within four weeks of treatment in all animals, which was reversible with cessation of treatment. On microscopic examination, normal skin histology was observed except for loss of pigmentation in the hair follicle/shaft. There was no loss of melanocytes. All phases of the hair cycle were present, and no inflammatory or degenerative changes in hair follicles, sebaceous glands, epidermis, or dermis were observed. In contrast to these observations in mouse and rabbit, no change in hair pigment or skin and retinal histology have been observed in monkeys treated for up to 9 months with MK-8931 at exposures 36-fold above those achieved at the highest dose of MK-8931 tested in P017 (60 mg). Furthermore, no adverse events of skin hypo- or depigmentation have been reported thus far in prior human trials of MK-8931.

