5.5 Dose and Administration Rationale

Subjects who tolerated study medication and completed the initial 78-week trial of Protocol 017 may enroll in this long term safety trial. Those subjects who did not complete treatment in the initial 78-week trial, but did continue in the trial and completed the scheduled visits, may be permitted to enroll in this long term safety trial. Subjects who received the 12 mg or 40 mg dose during the initial 78-week trial will continue to receive the same dose in this long term safety trial. They will be referred to as the 12/12 and the 40/40 groups respectively. Subjects who received placebo during the initial 78 week trial will receive the 40 mg dose during this long term safety trial. They will be referred to as the placebo/40 group.

The 40 mg dose has been shown to substantially inhibit CSF A β . The 12 mg dose produces a more moderate reduction in CSF A β and is included since the long term safety of greater inhibition is unknown. Using PK/PD modeling and simulation, 12 mg and 40 mg doses are projected to reduce CSF A β by at least 50% and 75%, respectively, in more than 90% of subjects. It is unknown how much A β lowering is optimal from the perspective of both safety/tolerability as well as efficacy. Subjects who received placebo during the initial 78 week trial will be treated with the 40 mg dose in the long term safety trial to provide additional information about the long term safety of MK-8931 and to estimate the clinical effects of delayed start of this higher dose.

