8.1 Subject Populations to be Analyzed

The analysis populations are the Full Analysis Set population, the Modified Full Analysis Set population and the All-Patients-as-Treated population.

- The Full Analysis Set (FAS) population will serve as the primary population for the analysis of efficacy data in this trial. The FAS population consists of all randomized subjects who have a baseline observation and at least one within-analysis-window (± 6 weeks) post-Randomization observation for the analysis endpoint subsequent to at least one dose of trial treatment. Subjects will be included in the treatment group to which they were randomized. Since the Sponsor's standing internal DMC (siDMC) reviewed unblinded analyses (including the ADAS-Cog) from the first 200 subjects enrolled in the initial 78-week trial, these subjects will be excluded from the FAS population, and hence all efficacy analyses.

All available observations from the initial 78-week trial will be included in the relevant model-based FAS analyses. Observations from the long term safety trial will be included according to the principles outlined above, with the following additional requirement: the subject must have taken at least one dose of study medication within the 28 days preceding Visit 10B and within the 28 days following Visit 10B.

- The Modified Full Analysis Set (MFAS) population will be utilized for sensitivity analyses and is defined identically to the FAS population with one exception: subjects will be required to have either 1) a baseline measurement for the analysis endpoint or 2) at least one within-analysis-window (± 6 weeks) post-dose, post-randomization observation for the analysis endpoint, but not necessarily both.
- The All-Patients-as-Treated (APaT) population will be used for the analysis of safety data in this trial. The APaT population consists of all randomized subjects who received at least one dose of trial treatment, with subjects included in the treatment group corresponding to the trial treatment they actually received. For most subjects this will be the treatment group to which they were randomized. Subjects who take incorrect trial treatment for the entire treatment period will be included in the treatment group corresponding to the trial treatment actually received. Since the siDMC reviewed unblinded analyses from the first 200 subjects enrolled in the initial 78-week trial, these subjects will be excluded from the primary safety analyses.

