8.4.2 Exposure

Basic summary statistics for the number of doses of trial medication taken will be calculated overall, and as well as over each 3-month time frame by treatment group. The cumulative percent of subjects taking various numbers of doses of trial medication (eg, one dose, 30 doses) will be calculated by treatment group. The APaT population will be used for all trial medication exposure calculations.

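### Safety is planned only on data pooled from Week 0, so placebo subjects' events after the switch to 40 mg count as comparator events and no planned AE table separates them

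*Combined protocol and SAP*

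**What the plan says.** The Synopsis (Safety Analysis) states: "Safety analyses will be conducted on the cumulative data from the initial 78-week trial pooled with the data from the long term safety trial". Section 8.3 repeats the rule and adds that "no analyses will be conducted on the long term safety trial alone". The section 8.3 sentence is itself damaged: its wording announces two data sets but names only the cumulative one.

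Section 8.3 says that, where applicable, "treatment comparisons will be conducted between the 40 mg / 40 mg and Pbo / 40 mg arms", and likewise between 12/12 and Pbo/40. The safety population in section 8.1 includes all randomized, treated subjects (the primary analyses leave out the first 200), "with subjects included in the treatment group corresponding to the trial treatment they actually received". That gives one group per subject, with no rule that assigns an event to the treatment being taken when it began. Table 8 gives Tier 1 endpoints a p-value and a 95% CI and Tier 2 endpoints a 95% CI. It has no onset period, person-time or time-to-event element, and the broad AE categories are percentages of subjects.

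Exposure is summarized separately in section 8.4.2: "Basic summary statistics for the number of doses of trial medication taken will be calculated overall", and by 3-month period and group. It is not linked to events. Section 8.0 says that no separate SAP will be issued. Section 5.5 gives as one reason for moving placebo subjects to 40 mg "to provide additional information about the long term safety of MK-8931".

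**The concern.** Safety and tolerability is the first primary objective (section 6.1). After Week 78 the Pbo/40 arm is a mixture: subjects who took only placebo, and subjects who took placebo and then 40 mg. In a cumulative count by randomized sequence, an event in a switcher's first weeks on 40 mg raises the comparator percentage. If MK-8931 causes events soon after the first dose, the difference between 40/40 and Pbo/40 shrinks once switchers are exposed, and nothing planned beside it shows why. Someone reading only the planned tables could not tell a Pbo/40 event on placebo from one on drug. Nor would they see the post-switch experience that section 5.5 offers as a reason for the switch.

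**Working it through.** **The plan's own figure.** Synopsis, Sample Size: 1960 × 0.70 × 0.90 = 1234.8, which reproduces the stated 1235.

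**Switchers.** Table 7 uses 570 per arm. With the same rates, 570 × 0.70 × 0.90 = 359 placebo subjects start 40 mg; 570 − 359 = 211 never do but stay in the same arm.

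**Simple model.** Let b be the background risk to Week 78, r an extra risk falling soon after the first 40 mg dose, and f = 0.63 the share entering the extension.

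- Placebo-controlled difference: (1 − b)r.
- Pooled difference to Week 104: (1 − b)(1 − f)r, because the background risk in the extension cancels.
- Ratio: 1 − f = 0.37, whatever b and r are.

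Example with b = 3%, r = 5% and a further background risk of 1% in Weeks 78-104 (all assumed): 4.85 points to Week 78. The pooled result is 8.43% vs 6.64%, or 1.79 points, and 1.79/4.85 = 0.37.

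**First-event model with dropout.**

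- From the documents: 570 per arm, 30% dropout by Week 78, 90% uptake, 45% dropout by Week 104. The weekly dropout rate is −ln(0.70)/78 to Week 78; 10% of completers leave at Week 78; then −ln(0.55/0.63)/26.
- Assumed: placebo hazard h = 0.001 per week (0.001 × 52 × 100 = 5.2 per 100 person-years), and crude proportions, because Table 8 names no method.
- Interval: difference ± 1.96 × √[p₁(1 − p₁)/570 + p₀(1 − p₀)/570].

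| Hazard on drug | Week | 40/40 vs Pbo/40 | Difference, points (95% CI) | z |
|---|---|---|---|---|
| 4h, first 26 weeks | 78 | 12.9% vs 6.3% | 6.6 (3.2 to 10.0) | 3.8 |
| | 104 | 14.2% vs 11.7% | 2.5 (−1.4 to 6.4) | 1.3 |
| 2h, first 26 weeks | 78 | 8.6% vs 6.3% | 2.3 (−0.8 to 5.3) | 1.45 |
| | 104 | 9.9% vs 9.1% | 0.9 (−2.5 to 4.3) | 0.49 |
| 2h throughout | 78 | 12.2% vs 6.3% | 5.9 (2.5 to 9.2) | 3.4 |
| | 104 | 14.8% vs 9.1% | 5.7 (1.9 to 9.4) | 3.0 |
| 2h only after 78 weeks | 78 | 6.3% vs 6.3% | 0 | 0 |
| | 104 | 9.1% vs 7.7% | 1.4 (−1.9 to 4.6) | 0.8 |

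Differences are taken before rounding. With no drug effect the difference is 0 at every time.

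**Reading the table.** Early onset keeps about 2.5/6.6 = 38% of the Week 78 difference, close to the simple model. A constant hazard keeps about 96% on the risk-difference scale, although the risk ratio falls from 1.93 to 1.62. Late-onset risk appears only in the pooled data.

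**The case against.** The case for leaving the plan alone has real weight.

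- **The pooled contrast works for most hazard shapes.** This stands. It compares the randomized sequences, is little changed for a constant hazard as a difference, and is needed for late onset. A reader might infer that it is invalid or hides harm in general; the table above does not support that.
- **Only one assumed scenario changes the inference.** This also stands. At an early hazard ratio of 2 the result is non-significant before and after the switch, and the documents give no safety event rates.
- **Direct evidence for early onset is thin.** Section 5.4 reports that "reduced hair pigment was observed within four weeks of treatment in all animals" in mouse and rabbit, but not in monkeys or, so far, in humans. The same section foresees a placebo versus MK-8931 look at hypopigmentation once 300 subjects per group reach six months. Hypopigmentation is not a Tier 1 endpoint. The documents cite nothing comparable for delirium or rash, and the MRI-based Tier 1 endpoints are less affected because routine MRI is not done in the extension.
- **First exposure to 40 mg is already observed under randomization in Weeks 0-78.** True, and the base-trial report may give it; the base protocol is not supplied. A reader might infer that early risk on 40 mg has no planned estimate anywhere. The documents support only that post-switch AEs have none in this plan.
- **Post-switch data are selected, later and uncontrolled.** This stands, and is why they should be labelled descriptive. A higher rate in switchers than in their earlier placebo time could reflect age or disease progression.
- **Oversight exists.** Section 8.2.8 says: "Additional safety analyses may be conducted throughout the trial as requested by the eDMC". That answers any inference of a subject-protection gap. It does not specify a table for the report.

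A reader might also take the ban on extension-only analyses to forbid a split by treatment at onset. It does not forbid a cumulative table split that way; it simply specifies none.

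**Conclusion.** The point holds as a reporting gap that should be fixed. The plan counts switchers' on-drug events as comparator events in the formal safety contrasts and specifies no AE summary that separates them. With 63% of the placebo arm projected to switch, excess risk confined to the weeks after first exposure would keep only about 37% to 38% of its placebo-controlled difference by Week 104. That figure rests on the plan's completion and uptake rates and on an assumed onset pattern. The percentage-point results also rest on the assumed hazard of 0.001 per week and 570 per arm. The dilution alters the conclusion for an assumed early hazard ratio of 4. It does not for an early ratio of 2, and it is negligible for a constant hazard on the difference scale.

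**What to change.** Keep the cumulative 40/40 and 12/12 versus Pbo/40 comparisons with their p-values and intervals, and label them early versus delayed start. Add two items:

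1. The same comparisons limited to onset in the placebo-controlled Weeks 0-78, or a citation to the base-trial report if it gives them.
2. A descriptive AE table by treatment being taken at onset, with exposure-adjusted incidence by arm and time since first MK-8931 dose. The Pbo/40 clock starts at the first extension dose. Label post-switch results descriptive, and say that extension entrants are a selected, later and uncontrolled group.

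Reword the sentences in the Synopsis and section 8.3 so that they clearly do not exclude these, and repair the section 8.3 sentence so that it names every data set it means.

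A re-baselined laboratory, ECG and vital-sign summary for switchers should be left out, or made conditional on pre-switch values existing. Visit 10B collects them only after a therapy gap of more than 3 months, and the Visit 10 schedule is not in these documents.

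The cost is a few extra tables from AE start dates (Table 4) and medication records (section 8.4.1) already collected; no visits or assessments change. The risk is over-reading uncontrolled post-switch rates, which the labelling is meant to limit.

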8.3.1 Analysis of Prespecified Safety Endpoints

The Prespecified Safety Endpoints of 1) microhemorrhage, superficial siderosis or macrohemorrhage in brain MRI scans, 2) vasogenic edema, 3) delirium, and 4) rash ECI are considered as Tier 1 events and will be analyzed as indicated in [Table 8](#).

Table 8 Analysis Strategy for Safety Parameters

Safety Tier	Safety Endpoint	P-Value	95% CI for Treatment Comparison	Descriptive Statistics
Tier 1	Incident microhemorrhage, superficial siderosis or macrohemorrhage in brain MRI scans	X	X	X
	Incident vasogenic edema	X	X	X
	Delirium	X	X	X
	Rash ECI	X	X	X
Tier 2	Any AE ^a		X	X
	Any Serious AE		X	X
	Any Fatal AE		X	X
	Any Drug-Related AE		X	X
	Any Serious and Drug-Related AE		X	X
	Discontinuation due to AE		X	X
	Specific AEs, SOCs, or PDLC (incidence \geq 1% in one of the treatment groups)		X	X
Tier 3	Specific AEs, SOCs or PDLC (incidence < 1% in all of the treatment groups)			X
	Change from Baseline Results (Labs, ECGs, Vital Signs)			X

AE=adverse event; CI=confidence interval; ECG=electrocardiogram; PDLC=predefined limit of change; SOC=system organ class; X=results will be provided.

a Adverse experience references refer to both clinical and laboratory AEs. Includes only those endpoints not prespecified as Tier 1 or not already prespecified as Tier 2 endpoints.

8.3.2 Analysis of Commonly Occurring Safety Endpoints

The broad clinical and laboratory AE categories consisting of the percentage of subjects with any AE, with a drug-related AE, with an SAE, with an AE which is both drug-related and serious, or who discontinued because of an AE are considered as Tier 2 endpoints and will be analyzed as indicated in [Table 8](#).

8.3.3 Analysis of Descriptive Safety Endpoints

Descriptive Safety Endpoints are considered as Tier 3 events and will be analyzed as indicated in [Table 8](#).

8.4 Trial Medication Compliance and Exposure

8.4.1 Compliance

As part of the routine recording of the amount of trial treatment taken by each subject, the number of pills remaining in trial packaging will be counted and recorded at regular intervals. These results will be used to calculate subject compliance. Instances where the subject took more or less trial medication than prescribed will be recorded on the study medication eCRF. Events that meet criteria for overdose as defined in [Section 7.7.2.2.4](#) will also be reported as an AE (ECI or SAE, as applicable). To monitor for potential misuse, the site will document significant discrepancies in drug returns where the subject or trial partner returns less trial medication than expected but denies taking extra trial medication (eg, lost or missing medication equivalent to more than one pill per week).

A day within the trial will be considered an “On-Therapy” day if the subject doses on that day. For a subject who is followed for the entire trial period, the “Number of Days Should be on Therapy” is the total number of days from the first dose to the last scheduled day for treatment administration for that subject. For a subject who permanently discontinued trial medication, the “Number of Days Should be on Therapy” is the total number of days from the first dose to the last dose of trial medication.

For each subject, percent compliance will be calculated as 100 times the number of days 'On Therapy" divided by the "Number of Days Should be on Therapy". The average compliance overall, and over each 3-month time frame, will be calculated by treatment group. The percent of subjects who meet various compliance thresholds (eg, 75%, 95% compliant) will also be calculated overall, and over each 3-month time frame, by treatment group. The FAS population will be used for all trial medication compliance calculations.

8.4.2 Exposure

Basic summary statistics for the number of doses of trial medication taken will be calculated overall, and as well as over each 3-month time frame by treatment group. The cumulative percent of subjects taking various numbers of doses of trial medication (eg, one dose, 30 doses) will be calculated by treatment group. The APaT population will be used for all trial medication exposure calculations.

8.5 Demography

Basic summary statistics (means, standard deviations, counts, percentages) will be provided, as applicable, by treatment group, for subject baseline characteristics, subject disposition, and prior and concomitant medication usage.

9.0 ADHERENCE TO ETHICAL, REGULATORY, AND ADMINISTRATIVE CONSIDERATIONS

The trial must be conducted in accordance with Good Clinical Practice (GCP) as outlined in the International Conference on Harmonisation of Technical Requirements for Registration of Pharmaceuticals for Human Use (ICH) Guidelines, E6 Good Clinical Practice: Consolidated Guidance and other applicable laws and regulations. In addition, the trial must be conducted in accordance with: (i) the USA Code of Federal Regulations (CFR) if the trial is conducted under a USA IND, regardless of the country involved; (ii) the European Union (EU) Clinical Trial Directive (CTD) and local regulations if the trial is conducted in the EU; and (iii) any specific local regulations if the trial is conducted elsewhere.

